1. COLORECTAL CANCER STARTS IN WHAT PART OF THE BODY?

Correct Answer: Colon and/or rectum

McNemar's chi2(1) = 0.00 Prob > chi2 = 1.0000

Exact McNemar significance probability = 1.0000

NOT SIGNIFICANT, THERE IS NOT A SIGNIFICANT DIFFERENCE IN THE CORRECT RESPONSES PRE AND POST SURVEY.

Pre Starts in what body part	Post Starts in what body part			Grand Total
	Null	Colon and or rectum	Small Intestine	
Null	2	4	1	7
Colon and or rectum	1	56	10	69
Small Intestine	1	8	10	20
Stomach		1	1	2
Grand Total	4	69	22	100

2. A STOOL TEST (FIT/FOBT) CHECKS YOUR STOOL (POOP) FOR?

Correct Answer: Blood

McNemar's chi2(1) = 3.20 Prob > chi2 = 0.0736

Exact McNemar significance probability = 0.1153

NOT SIGNIFICANT, THERE IS NOT A SIGNIFICANT DIFFERENCE IN THE CORRECT RESPONSES PRE AND POST SURVEY.

Pre Checks stool for	Post Checks stool for					Grand Total
	Null	Blood	Fat	Polyps	Tumors	
Null	3	6		4	1	14
Blood	2	60	2	1	1	66
Fat		2				2
Polyps	1	5		9	1	16
Tumors		1		1		2
Grand Total	6	74	2	15	3	100

3. WHICH OF THE FOLLOWING ARE RISK FACTORS FOR COLORECTAL CANCER? PLEASE CHECK ALL THAT ARE CORRECT.

Correct Answer: Count of 5

McNemar's chi2(1) = 21.78 Prob > chi2 = 0.0000

Exact McNemar significance probability = 0.0000

SIGNIFICANT, THERE IS A SIGNIFICANT DIFFERENCE IN THE CORRECT RESPONSES PRE AND POST SURVEY.

Pre Num..	Post Number of Risk Factors					Grand Total
	1	2	3	4	5	
0		1			3	4
1	1	1		3	8	13
2		5	4	3	7	19
3	2		2	1	6	11
4			1		8	9
5			1	3	40	44
Grand Total	3	7	8	10	72	100

4. IN GENERAL, A COLONOSCOPY SHOULD BE PERFORMED EVERY 10 YEARS STARTING AT AGE:

Correct Answer: 50

McNemar's chi2(1) = 13.00 Prob > chi2 = 0.0003

Exact McNemar significance probability = 0.0002

SIGNIFICANT, THERE IS A SIGNIFICANT DIFFERENCE IN THE CORRECT RESPONSES PRE AND POST SURVEY.

Pre Colonoscopy ..	Post Colonoscopy Starting age				Grand Total
	30	40	50	60	
Null				1	1
30	3		1		4
40		4	11		15
50			79		79
60			1		1
Grand Total	3	4	92	1	100

5. IN GENERAL, A STOOL (POOP) TEXT (FIT OR FOBT) SHOULD BE DONE EVERY YEAR STARTING AT AGE:

Correct Answer: 50

McNemar's chi2(1) = 20.16 Prob > chi2 = 0.0000

Exact McNemar significance probability = 0.0000

SIGNIFICANT, THERE IS A SIGNIFICANT DIFFERENCE IN THE CORRECT RESPONSES PRE AND POST SURVEY.

Pre stool test start age	Post Stool test starting age					Grand Total
	Null	30	40	50	60	
Null	1			9		10
30		3	2	2		7
40	1	1	8	7		17
50		1	2	44		47
60			1	10	8	19
Grand Total	2	5	13	72	8	100

6. LYNCH SYNDROME IS A DISORDER THAT RUNS IN FAMILIES AND INCREASES MY CHANCES OF DEVELOPING COLORECTAL CANCER.

Correct Answer: True

McNemar's chi2(1) = 29.45 Prob > chi2 = 0.0000

Exact McNemar significance probability = 0.0000

SIGNIFICANT, THERE IS A SIGNIFICANT DIFFERENCE IN THE CORRECT RESPONSES PRE AND POST SURVEY.

		Post Lynch Syndrome increases risk			Grand Total
		Null	False	True	
Pre Lync..	Null	5	2	23	30
	False	8	1	17	
True	3	1	48	52	
Grand Total	8	4	88	100	

7. THE EARLIER THAT COLORECTAL CANCER IS FOUND, THE GREATER MY CHANCES OF SURVIVAL.

Correct Answer: True

McNemar's chi2(1) = 2.00 Prob > chi2 = 0.1573

Exact McNemar significance probability = 0.5000

NOT SIGNIFICANT, THERE IS NOT A SIGNIFICANT DIFFERENCE IN THE CORRECT RESPONSES PRE AND POST SURVEY.

		Post Earlier found, greater survival		Grand Total
Pre Earlier Found, greater survival		Null	True	
Null	Null	1	2	3
	True		97	97
Grand Total		1	99	100

8. EVEN IF I HAVE NO SYMPTOMS, I MAY STILL HAVE COLORECTAL CANCER.

Correct Answer: True

McNemar's chi2(1) = 5.40 Prob > chi2 = 0.0201

Exact McNemar significance probability = 0.0352

SIGNIFICANT, THERE IS A SIGNIFICANT DIFFERENCE IN THE CORRECT RESPONSES PRE AND POST SURVEY.

Pre No s..	Null	Post No symptoms		Grand Total
		False	True	
Null	1		8	9
False			4	4
True	2	1	84	87
Grand Total	3	1	96	100

9. POLYPS ARE GROWTHS IN THE LINING OF THE COLON OR RECTUM THAT CAN DEVELOP INTO COLORECTAL CANCER.

Correct Answer: True

McNemar's chi2(1) = 0.00 Prob > chi2 = 1.0000

Exact McNemar significance probability = 1.0000

NOT SIGNIFICANT, THERE IS NOT A SIGNIFICANT DIFFERENCE IN THE CORRECT RESPONSES PRE AND POST SURVEY.

Pre Poly..	Null	Post Polyps are growths		Grand Total
		False	True	
Null		1	2	3
True		1	95	97
Grand Total		2	97	100

10. A COLONOSCOPY CAN BE USED TO FIND POLYPS IN THE COLON AND RECTUM.

Correct Answer: True

McNemar's chi2(1) = 1.00 Prob > chi2 = 0.3173

Exact McNemar significance probability = 1.0000

NOT SIGNIFICANT, THERE IS NOT A SIGNIFICANT DIFFERENCE IN THE CORRECT RESPONSES PRE AND POST SURVEY.

Pre Colo..	Null	Post Colonoscopy finds polyps		Grand Total
		True	False	
Null		1		1
False			1	1
True		98		98
Grand Total		1	99	100

11. A DIET HIGH IN RED MEATS AND PROCESSED MEATS (LUNCH MEATS, HOT DOGS) INCREASES MY CHANCES OF DEVELOPING COLORECTAL CANCER.

Correct Answer: True

McNemar's $\chi^2(1) = 3.00$ Prob > $\chi^2 = 0.0833$

Exact McNemar significance probability = 0.1460

NOT SIGNIFICANT, THERE IS NOT A SIGNIFICANT DIFFERENCE IN THE CORRECT RESPONSES PRE AND POST SURVEY.

Pre Meat..	Null	Post Meat increase cancer		Grand Total
		False	True	
Null	1		5	6
False		2	4	6
True	1	2	85	88
Grand Total	2	4	94	100

12. IT IS OK TO SKIP COLORECTAL CANCER SCREENING IF I DO NOT HAVE ANY SYMPTOMS.

Correct Answer: False

McNemar's chi2(1) = 0.33 Prob > chi2 = 0.5637

Exact McNemar significance probability = 0.7744

NOT SIGNIFICANT, THERE IS NOT A SIGNIFICANT DIFFERENCE IN THE CORRECT RESPONSES PRE AND POST SURVEY.

Pre Skip ..	Null	Post Skip Screening		Grand Total
		False	True	
Null		1	2	3
False		87	7	94
True		3		3
Grand Total		1	92	100

13. MY CHANCES OF DEVELOPING COLORECTAL CANCER ARE HIGHER IF SOMEONE IN MY IMMEDIATE FAMILY HAS IT OR HAS HAD IT.

Correct Answer: True

McNemar's $\chi^2(1) = 4.50$ Prob > $\chi^2 = 0.0339$

Exact McNemar significance probability = 0.0703

Chi² is significant, but Exact p-value is not significant. Since the Incorrect responses (when added together) have a cellsize <4, then the Exact P-value should be used.

NOT SIGNIFICANT, THERE IS NOT A SIGNIFICANT DIFFERENCE IN THE CORRECT RESPONSES PRE AND POST SURVEY.

Pre Fami..	Null	Post Familial risk		Grand Total
		False	True	
Null	1		3	4
False			4	4
True		1	91	92
Grand Total	1	1	98	100

14. INCREASING MY PHYSICAL ACTIVITY WILL NOT LOWER MY CHANCES OF DEVELOPING COLORECTAL CANCER.

Correct Answer: False

McNemar's $\chi^2(1) = 5.83$ Prob > $\chi^2 = 0.0158$

Exact McNemar significance probability = 0.0241

SIGNIFICANT, THERE IS A SIGNIFICANT DIFFERENCE IN THE CORRECT RESPONSES PRE AND POST SURVEY.

Pre Physi..	Null	Post Physical activity NOT lower risk		Grand Total
		False	True	
Null		1	5	7
False		60	8	68
True		16	9	25
Grand Total		1	81	100

TOTAL NUMBER OF CORRECT ANSWERS

Pre Total..	Post Total Correct Answers							Yes	Grand T..
	8	9	10	11	12	13	Yes		
4		1							1
6			1	1					2
7	1		1				1		3
8	1	1		2	1	1			6
9			2		4				6
10	2	2	4	7	3	4			22
11			2		8	6			16
12				5	9	10			24
13				2	5	5			12
14			1		1	5			7
Yes							1	1	
Grand To..	4	4	11	17	31	32	1	100	

Wilcoxon Signed Rank Test

Sign	Obs	Sum ranks	Expected
Positive	25	1318	2420
Negative	55	3522	2420
Zero	20	210	210
All	100	5050	5050

unadjusted variance 84587.50

adjustment for ties -2388.38

adjustment for zeros -717.50

adjusted variance 81481.63

Ho: preTotalCorrect = postTotalCorrect

z = -3.861

Prob > |z| = 0.0001

SIGNIFICANT, THERE IS A SIGNIFICANT DIFFERENCE IN THE TOTAL CORRECT RESPONSES PRE AND POST SURVEY.

SUMMARY STATISTICS

Pre Total Correct Answers

	Percentiles	Smallest		
1%	2.5	1		
5%	7	4		
10%	8	6	Obs	100
25%	10	6	Sum of Wgt.	100
50%	11		Mean	10.78
75%	12	14	Std. Dev.	2.195404
90%	13	14	Variance	4.819798
95%	14	14	Skewness	-1.335507
99%	14	14	Kurtosis	6.343168

Post Total Correct Answers

	Percentiles	Smallest		
1%	4.5	1		
5%	8.5	8		
10%	10	8	Obs	100
25%	11	8	Sum of Wgt.	100
50%	12		Mean	11.54
75%	13	13	Std. Dev.	1.719878
90%	13	13	Variance	2.95798
95%	13	13	Skewness	-2.702217
99%	13	13	Kurtosis	15.56301

Variable	Obs	Mean	Std. Dev.	Min	Max
preTotalCorrect	100	10.78	2.195404	1	14
postTotalCorrect	100	11.54	1.719878	1	13

The 1st column is Total Correct Answers Post – Pre. So, one person (Freq column) had 4 more correct answers on the pre test and one person had 6 more correct answers Post. In most cases (29), people had one more correct answer.

Post – Pre Total Correct	Freq.	Percent	Cum.
-4	1	1.00	1.00
-2	5	5.00	6.00
-1	19	19.00	25.00
0	20	20.00	45.00
1	29	29.00	74.00
2	9	9.00	83.00
3	11	11.00	94.00
4	2	2.00	96.00
5	3	3.00	99.00
6	1	1.00	100.00
Total	100	100.00	

INTENT

No analysis was done on the intent questions as they were only asked one time.

Intent

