Through this project, NCI/CRCHD intends to answer the following question: Did the colorectal cancer outreach activity change participants' knowledge of colorectal cancer, risk factors, and screening options and recommendations?

3. Study Design

Describe all study procedures, materials, and methods of data collection:

Format and Sites:

NCCC's Community Health Educators ([name] and [name]) will coordinate two to six group education activities/events in New Hampshire and Vermont starting in March 2017. Elements of the group education have been designed by NCI/CRCHD and center around a set of key messages that cover information about colorectal cancer, including incidence, risk factors, prevention, screening recommendations, and screening options (see attached PDF *NCI Colorectal Cancer Outreach and Screening Initiative Toolkit*, pgs. 3-4 and PowerPoint presentation *Screen to Save: Colorectal Cancer Basics*). Where feasible, education may also include information about local options for getting screened for colorectal cancer. Depending on the setting, education will be delivered to participants using one or more of the following educational tools: inflatable colon with educational signage, a PowerPoint presentation, a flipchart/flipbook, written materials/handouts, and verbal instruction. Education will take place in a variety of settings such as community-based organizations (e.g., community businesses, libraries, faith-based organizations, senior centers), fairs and community events, and clinical centers (e.g., health centers, local hospitals). We plan to conduct our first group education activity and data collection effort at the WZID Women's Expo in Manchester, NH on March 11, 2017. Dartmouth-Hitchcock is a sponsor of the event.

Eligible Participants and Data Collection:

Anyone, regardless of age, is welcome and encouraged to participate in the educational activities. However, our research team will be recruiting 100 to 150 people aged 50-74 years old at the time of the event to participate in the evaluation/data collection efforts. At the outreach event, each person recruited will be asked to:

- 1) Review our study information sheet with a CITI-trained research team member

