STATISTICAL ANALYSIS PLAN WITH RESULTS

Screen to Save: A Colorectal Cancer Educational Intervention

NCT03907579

Date: July 8, 2020

ANALYSIS - BACKGROUND

For the Screen2Save intervention, subjects first take a survey, participate in the intervention and then take a final survey. The questions are the same on both surveys. All analysis was done using Stata/SE 15.1.

DID THE INTERVENTION CHANGE THE SURVEY RESULTS?

We are most interested in whether the subjects scored better (had more correct answers) in the post survey than the pre survey. Thus, for analysis purposes, each question was coded as a dichotomous Correct or Not Correct. If a subject did not submit a response for the question, it was coded as Not Correct (we may want to revisit this).

In order to test whether there was a difference in the Correct responses in the pre and post tests, McNemar's Test was used.

The McNemar test is a non-parametric test for paired nominal data. It's used when you are interested in finding a change in proportion for the paired data. For example, you could use this test to analyze retrospective case-control studies, where each treatment is paired with a control. It could also be used to analyze an experiment where two treatments are given to matched pairs. This test is sometimes referred to as McNemar's Chi-Square test because the test statistic has a chi-square distribution. (<https://www.statisticshowto.com/mcnemar-test/>)

When sample sizes are small, the chi-squared value may not be well-approximated by the chi-squared distribution. The exact p-value can be computed.

Thus, for each pair of pre and post questions, McNemar's Test was performed and both the Chi² and the exact P-value are shown. If the p-value is significant (<0.05), then the null hypothesis (H₀ = the number of correct responses on the pre survey are the same as on the post survey) can be rejected.

HOW DID THE SURVEY RESPONSE CHANGE?

Although the primary interest is whether the intervention increased knowledge about Colorectal cancer and screening, understanding what the specific responses were to the surveys is also of interest. CrossTab tables help to both quantify and visualize the relationship between the Pre and Post responses. The Pre responses are shown in the rows while the Post responses are in the columns. The light green to dark blue color gradient highlights the low to high number of responses for each category.

Did the intervention increase the number of correct answers?

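### Question 3 is tested only as all five risk factors ticked versus fewer, so the recorded 0-5 count enters no estimate or test and 16 of 100 participants whose count changed are treated as unchanged

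*SAP*

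**What the plan says.** The SAP's section on whether the intervention changed the survey results applies one scoring rule to all 14 questions: "each question was coded as a dichotomous Correct or Not Correct". A blank is scored as wrong: "If a subject did not submit a response for the question, it was coded as Not Correct". Each question then gets the same test: "for each pair of pre and post questions, McNemar's Test was performed and both the Chi² and the exact P-value are shown".

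Question 3 asks participants to mark every risk factor on a list ("PLEASE CHECK ALL THAT ARE CORRECT"), and the SAP gives "Correct Answer: Count of 5" as the only correct response. The printed result is "McNemar's chi2(1) = 21.78 Prob > chi2 = 0.0000", labelled significant. Below it is a crosstab of the number of risk factors, 0 to 5 before by 1 to 5 after. The SAP gives no reason for the cut at five and no estimate or test on the count.

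The Protocol (section 2, Objectives and Hypotheses) asks whether the activity did "change participants' knowledge of colorectal cancer, risk factors, and screening options and recommendations". Risk factors are thus a named part of the study question.

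**The concern.** Question 3 yields a graded response, and the cut at five reduces it to all or nothing. A participant who goes from one box to four is scored wrong both times. A participant with four boxes scores the same as one with none. A move from four to five counts as much as a move from zero to five, and a drop from five to four counts as a complete loss.

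Two things are at stake. The first is the description of the effect on a named part of the study question: the test says whether more people ticked all five, but not how many more risk factors were ticked or by how many people. The second is precision, because a dichotomy usually uses less of the information in a graded score.

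The count also records how many boxes were ticked, not which ones. A reader cannot see which risk factors were learned.

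**Working it through.** **Inputs.** SAP, Question 3 crosstab (rows before, columns after):

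| Before | After 1 | 2 | 3 | 4 | 5 | Total |
|---|---|---|---|---|---|---|
| 0 | 0 | 1 | 0 | 0 | 3 | 4 |
| 1 | 1 | 1 | 0 | 3 | 8 | 13 |
| 2 | 0 | 5 | 4 | 3 | 7 | 19 |
| 3 | 2 | 0 | 2 | 1 | 6 | 11 |
| 4 | 0 | 0 | 1 | 0 | 8 | 9 |
| 5 | 0 | 0 | 1 | 3 | 40 | 44 |
| Total | 3 | 7 | 8 | 10 | 72 | 100 |

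All row and column totals agree with the printed ones.

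**1. The plan's own figure.** Gains to five: 3 + 8 + 7 + 6 + 8 = 32. Losses from five: 1 + 3 = 4. McNemar without continuity correction is (32 − 4)² / (32 + 4) = 784 / 36 = 21.78, as printed, so z = 28 / 6 = 4.67. The exact two-sided p is 1.9 × 10⁻⁶, printed as 0.0000.

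**2. What the cut leaves out.** Below five both times: 100 − 32 − 4 − 40 = 24.
- Unchanged: 1 + 5 + 2 = 8.
- Up: 0→2 (1), 1→2 (1), 1→4 (3), 2→3 (4), 2→4 (3), 3→4 (1), total 13.
- Down: 3→1 (2), 4→3 (1), total 3.

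So 16 people changed but are concordant in McNemar's test. The 32 scored gains are of +1 to +5 boxes (8, 6, 7, 8 and 3 people), all weighted equally.

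**3. The count.** Change (after − before):

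| Change | −2 | −1 | 0 | +1 | +2 | +3 | +4 | +5 |
|---|---|---|---|---|---|---|---|---|
| People | 3 | 4 | 48 | 14 | 10 | 10 | 8 | 3 |

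- 45 up, 7 down, 48 equal.
- The changes sum to 101 and their squares to 363. Mean change is 1.01 (3.40 to 4.41).
- SD = √[(363 − 101²/100) / 99] = 1.62; SE = 0.162.
- 95% CI = 1.01 ± 1.984 × 0.162 = 0.69 to 1.33.
- Estimate/SE = 6.22.
- Wilcoxon signed-rank |z| is 5.44 with zeros kept in the ranking, 5.29 with zeros dropped and 5.19 with zeros split. The SAP's printed zero adjustment for the total, 717.50 = 20 × 21 × 41 / 24, matches the first of these.

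**4. Precision of the two scores.** For the dichotomy, the change is 0.28, SD = √[(36 − 28²/100) / 99] = 0.533, and estimate/SE = 0.28 / 0.0533 = 5.25.
- Squared signal-to-noise ratio: (6.22 / 5.25)² = 1.40. The bootstrap 95% range is about 0.87 to 2.57, with about 90% of resamples above 1.
- Wilcoxon against McNemar: (5.19 / 4.67)² = 1.24 to (5.44 / 4.67)² = 1.36.

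**5. If the four pre-test zeros are blanks.** They contribute 2 + 3 × 5 = 17 of the 101 points. Without them, the mean change is 84 / 96 = 0.88. The squares sum to 363 − 4 − 75 = 284, so SD = √[(284 − 84²/96) / 95] = 1.49 and SE = 0.152. The 95% CI is 0.57 to 1.18.

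**6. Question 3 in the total.** The 14 pre-test correct counts, with Question 3 entered as 44, sum to 1078, the stated mean of 10.78 × 100. Question 3 therefore enters the total as one right/wrong item.

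**The case against.** Scoring a check-all item as fully right or not is a recognised choice. Here it follows from a uniform rule for all 14 questions, and the conclusion for Question 3 does not depend on it. That stands.

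A reader might infer that partial learning was concealed. The documents do not support this: the SAP prints the full count table, and every figure above comes from it. The counts are displayed but not used in an estimate or test. Nor does the SAP claim an effect of 28 percentage points. That figure is a subtraction of the table margins (72 − 44); the SAP prints only test results, the label and the table.

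A reader might also take the ratio of 1.40 to mean that the cut wastes information worth 40% more participants. This is too strong. The bootstrap range includes 1, the ratio falls to 1.24–1.36 when the two rank-type tests are compared, and ticking all five and the mean count are different estimands.

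The strongest objection is to the count itself. The questionnaire is not among the documents available for this review. No count exceeds five on 200 forms, which would fit a list of five true options with no distractor, but that is an assumption. If it is right, a higher count may partly reflect ticking more boxes. Other questions with blanks show a null row and Question 3 does not, so the four pre-test zeros may be non-responses. Both points stand. They are reasons to score the factors one by one and not to let the mean count replace the all-five result.

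**Conclusion.** The point holds as a matter of description and probable precision. The Question 3 test and the total leave out 16 participants whose count changed and ignore the size of every gain. The 16 is exact and rests only on the printed table. On the count, the change is +1.01 risk factors (95% CI 0.69 to 1.33), or +0.88 (0.57 to 1.18) if the four pre-test zeros are set aside. The count is probably the more precise measure, but 100 participants do not settle that.

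The documents do not support a claim that the Question 3 result is wrong. It is significant in the same direction on either score.

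Reading the change as risk factors recognised assumes that every counted option is a true risk factor, which the documents do not let a reader confirm.

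**What to change.** Keep the all-five McNemar result. Because the SAP already contains results, add the following, labelled post hoc:

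1. Score each risk factor separately as yes/no before and after, from the raw data that the Protocol (section 4, Analysis) says were returned to the site. Check the form for distractors, and state what a count of zero means.
2. Report the paired mean change in count with its 95% CI and the Wilcoxon signed-rank test already used for the total. Add a sensitivity analysis without the four pre-test zeros.
3. Show Question 3 as count/5 in the total as a sensitivity analysis only. First check the post-test total: the 14 post-test correct counts sum to 1223, while the stated mean of 11.54 implies 1154. The gap of 69 equals the Question 1 post-test count, so Question 1 may have been left out.

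The cost is a few lines of Stata on data already held, with no new data collection. The downside is a small amount of extra post hoc analysis, which the label makes plain.

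### Does one identical not-significant line for eight different items, with no paired change or confidence interval, leave the item results misleading?

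*SAP*

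**What the plan says.** Under *Did the intervention change the survey results?* the SAP states its question: "We are most interested in whether the subjects scored better (had more correct answers) in the post survey than the pre survey". For this, "each question was coded as a dichotomous Correct or Not Correct". A blank counts as not correct, a rule that the SAP itself marks as open to a second look. The decision rule opens with "If the p-value is significant (<0.05), then the null hypothesis".

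Each item then shows the McNemar chi-square and its p-value, the exact p-value, a verdict line and a crosstab. Under *How did the survey response change?* the SAP says what the tables are for: "CrossTab tables help to both quantify and visualize the relationship between the Pre and Post responses".

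Questions 1, 2, 7, 9, 10, 11, 12 and 13 all carry the line "NOT SIGNIFICANT, THERE IS NOT A SIGNIFICANT DIFFERENCE IN THE CORRECT RESPONSES PRE AND POST SURVEY". Questions 3, 4, 5, 6, 8 and 14 carry the opposite line. Only Question 13 has an added remark: the two tests disagree there and, for that item, "then the Exact P-value should be used". No item has a printed paired change or interval.

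**The concern.** The SAP asks whether people scored better, which is a question of direction and size, yet the item result is a yes/no line. The same wording covers at least three situations.

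- **Ceiling.** On Questions 7, 9 and 10 almost everyone was right beforehand, so improvement alone could not have reached the threshold.
- **Inconclusive gains.** Questions 2, 11 and 13 moved up by 6 to 8 points.
- **No net gain or a small fall.** Question 1 had as many losses as gains, and Question 12 went down by 2. Question 9, with 2 gains and 2 losses, belongs here as well as under ceiling.

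A reader who took only the verdict lines might conclude that the education did nothing on all eight topics. On some of them there was no room to show a gain, and on others a worthwhile gain is not excluded.

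**Working it through.** **Inputs.** Gains b (not correct, then correct) and losses c (correct, then not correct) come from the SAP crosstabs, n = 100. Where a table is broken in the text, the margins supply the missing cell. Question 9, for example, has 97 correct before, 97 after and 95 both times, so c = 97 - 95 = 2 and b = 97 - 95 = 2.

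**Step 1: reproduce the printed tests.** Chi-square = (b - c)²/(b + c). The exact p is the two-sided binomial on b + c pairs with probability 0.5.

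- Question 7: (2 - 0)²/2 = 2.00; exact p = 2 × 0.5² = 0.50. Printed: 2.00 and 0.5000.
- Question 2: (14 - 6)²/20 = 64/20 = 3.20. Printed: 3.20.
- Question 13: (7 - 1)²/8 = 4.50; exact p = 2 × (1 + 8)/256 = 0.0703. Printed: 4.50 and 0.0703.

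All 14 items agree with the printed values to the decimals shown.

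**Step 2: paired change and interval.** The change is (b - c)/100. The 95% interval is the Tango score interval: all d with |b - c - nd| / √(n(2q + d(1 - d))) ≤ 1.96, where q = [√(B² - 4AC) - B]/(2A), A = 2n, B = -b - c + (2n - b + c)d and C = -cd(1 - d).

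| Question | Correct pre | Correct post | b | c | Chi-square | Exact p | Change in points (95% interval) |
|---|---|---|---|---|---|---|---|
| 1 | 69 | 69 | 13 | 13 | 0.00 | 1.0000 | 0 (-10.3 to 10.3) |
| 2 | 66 | 74 | 14 | 6 | 3.20 | 0.1153 | +8 (-0.8 to 17.3) |
| 3 | 44 | 72 | 32 | 4 | 21.78 | 0.0000 | +28 (17.5 to 38.6) |
| 4 | 79 | 92 | 13 | 0 | 13.00 | 0.0002 | +13 (7.8 to 21.0) |
| 5 | 47 | 72 | 28 | 3 | 20.16 | 0.0000 | +25 (15.4 to 35.1) |
| 6 | 52 | 88 | 40 | 4 | 29.45 | 0.0000 | +36 (24.8 to 46.8) |
| 7 | 97 | 99 | 2 | 0 | 2.00 | 0.5000 | +2 (-1.8 to 7.0) |
| 8 | 87 | 96 | 12 | 3 | 5.40 | 0.0352 | +9 (1.6 to 17.4) |
| 9 | 97 | 97 | 2 | 2 | 0.00 | 1.0000 | 0 (-5.3 to 5.3) |
| 10 | 98 | 99 | 1 | 0 | 1.00 | 1.0000 | +1 (-2.7 to 5.4) |
| 11 | 88 | 94 | 9 | 3 | 3.00 | 0.1460 | +6 (-0.9 to 13.8) |
| 12 | 94 | 92 | 5 | 7 | 0.33 | 0.7744 | -2 (-9.6 to 5.4) |
| 13 | 92 | 98 | 7 | 1 | 4.50 | 0.0703 | +6 (0.6 to 12.9) |
| 14 | 68 | 81 | 21 | 8 | 5.83 | 0.0241 | +13 (2.6 to 23.6) |

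**Step 3: ceiling.** If all k people not correct at pre-test improved and nobody was lost, exact p = 2 × 0.5^k. For k = 3 (Questions 7 and 9) this is 0.25; for k = 2 (Question 10) it is 0.50. Five one-way changes give 0.0625 and six give 0.03125, so at least six are needed. Question 12 has exactly six.

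**Step 4: would the intervals alter a verdict?** At d = 0, C = 0 and q = (b + c)/(2n), so the score statistic is (b - c)/√(b + c), the signed root of the McNemar chi-square. The interval therefore excludes zero exactly when the chi-square p is below 0.05. It must agree with the printed chi-square p on all 14 items. It departs from the exact p only on Question 13, where the SAP already prints both p-values and says which it uses.

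**Step 5: what is already visible.** Because n = 100, the two *Correct* columns above are simply the crosstab margins. The change is one subtraction, and the room to improve is 100 minus the pre-test count.

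**The case for a change.** The strongest case for a change is that precision is not printed and cannot be read off the margins. The upper limits do differ: Question 2 still allows a gain of 17.3 points and Question 1 one of 10.3, while Question 12 allows only 5.4. The additions would be cheap and need no new data. That stands, and an author preparing a paper would do well to include them.

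It falls short of a reason to change the plan. The verdict line does not assert equality or absence of benefit, and it sits next to the full table. The SAP is dated July 2020 and already contains the results, so an added interval would be description after the fact.

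The column would also need its own caveats. Five upper limits exceed the largest gain that this sample could show: 7.0 against 3 points on Question 7, 5.3 against 3 on Question 9, 5.4 against 2 on Question 10, 13.8 against 12 on Question 11 and 12.9 against 8 on Question 13. This is legitimate inference about a population, but it reads oddly beside a ceiling label. On Question 13 the interval excludes zero while the SAP's chosen exact test does not, so the new column would reopen a conflict that the SAP has already settled.

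The blanks are a separate matter. All 3 not-correct answers at pre-test on Questions 7 and 9, and 1 of 2 on Question 10, were blanks. How to code them is a missing-data question that the SAP raises itself, and an interval does not answer it.

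I do not use the total score as a defence. The item margins sum to 1,078 before (10.78 per person, as printed) but 1,223 after (12.23, against a printed mean of 11.54). That mismatch is a separate question and does not touch the item tests.

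**Conclusion.** No change to the plan. The description is accurate: eight items share one line, and no paired change or interval is stated. But every item-level chi-square, p-value and verdict is correct, and direction, size and ceiling can be read from tables that the SAP provides for that purpose. The one conflict between tests, on Question 13, is disclosed. What is missing is a measure of precision, a reporting choice that an analyst can fill sensibly in a paper. Its effect on the 14 printed item verdicts is nil.

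This rests on three assumptions. The counts rebuilt from margins where the table text is broken are taken as right, which the match with all 14 printed tests supports. The intervals depend on the score method; on Question 13 another method, inverting the exact test, gives -0.4 to 7.9. Participants are treated as independent, although the protocol recruits at two to six group events; the documents give no event-level data, so any effect of that on the widths is unknown.
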